1.5 Sample Size

The duration of this observational study will depend on the rate of inclusion. Based on our previous experience from a European retrospective study, and on the increasing prenatal detection rate of cardiac defects, it is estimated that 10-20 intervention cases can be included each year. Inclusion rate of non-intervention cases will depend on how many non-intervention

Protocol

Statistical Analysis Plan

Effect of fetal aortic valvuloplasty on outcomes

Version:1.0Page 11 of 26

centers decide to join the study and on the proportion of subjects offered intervention who choose to refrain. It is projected that at least half as many non-intervention cases can be included each year. The study plans to end when 100 FAV cases are enrolled and at least 50 no-FAV cases, or 5 years from the first included patient, whichever occurs first.

The power calculations below are performed applying two-sided Fisher's exact test. The main analyses, however, will require adjusted analyses due to the study design being observational and not randomized. The confounders and their relation to the outcome and the main exposure variable are not completely known at the time of the study planning. Therefore, simplified power calculations were performed in order to assure that the study has potential to answer the main posed questions.

Inclusion of 100 intervention cases and 50 controls

The aim is to include at least 100 fetuses in the FAV 1+2 groups and 50 in the comparison group no-FAV 1+2. The largest numbers will likely be in FAV 1 and no-FAV 1 while the numbers in groups FAV 2 and probably also in no-FAV 2 will be smaller.

Assuming number of fetuses included as per above, 150 in total, and 30% success rate for the primary endpoint (=transplantation-free survival from fetal diagnosis to 2 years postnatal age, having a biventricular circulation without pulmonary hypertension at that time) in the no-FAV 1+2 group and 60% success rate in the FAV 1+2 group, using alpha 0.05 and two-sided Fisher's exact test, a power of 91.8% would be able to be achieved. For a power of at least 80%, and all other assumptions unchanged, a success rate of 56% vs 30% in the FAV and no-FAV group, respectively, would be needed to be observed.

Inclusion of 100 intervention cases and 100 controls

Assuming number of fetuses included as per above, 200 in total, and 30% success rate for the primary endpoint in the no-FAV 1+2 group and 60% success rate in the FAV 1+2 group, using alpha 0.05 and two-sided Fisher's exact test, a power of 98.7% would be able to be achieved. For a power of at least 80%, and all other assumptions unchanged, a success rate of 51% vs 30% in the FAV and no-FAV group, respectively, would be needed to be observed.

STATISTISKA KONSULTGRUPPEN	Statistic
Protocol:	Protocol No:
Effect of fetal aortic valvuloplasty on outcomes	

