Cases with termination of pregnancy after study inclusion will be excluded from analysis but numbers noted.

Subgroup analyses will be performed for:

- Subjects with diagnosis of fetal aortic stenosis that undergo technically successful fetal aortic valvuloplasty and additional fetal cardiac intervention(s) such as atrial septal balloon dilatation or stent placement.
- b. Subjects with diagnosis of fetal aortic stenosis and hydrops.
- c. Subjects with diagnosis of fetal aortic stenosis, severe mitral regurgitation and left atrial enlargement with or without restrictive or intact atrial communication and with or without hydrops.

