2 STUDY POPULATIONS

2.1 Definition of Study Populations

2.1.1 Full Analysis Set for All Enrolled

Fetuses with severe MR and severe LA enlargement and/or intact or highly restrictive interatrial communication and/or cases with hydrops present at inclusion are all high-risk cases regarding survival, but may have a rather good prognosis if they survive the first critical period. It is likely they will be overrepresented in the FAV group to such a degree that it will be difficult to control for through propensity score matching. Therefore this subpopulation will be excluded from the full analysis set and analysed separately. Fetuses developing any of these conditions after inclusion will not be excluded from the full analysis set.

All enrolled fetuses that have satisfied inclusion/exclusion criteria and belong to FAV 1+2 and no-FAV 1+2 groups and not listed as belonging to the high-risk population described above will be included in the Full Analysis Set enrolled (FAS_{ENR}) population. Infants wrongly included in the study (not fulfilling all inclusion or fulfilling any of the exclusion criteria) will not be part of the FAS_{ENR} population, but will be described in the safety analyses. As detailed under 1.3.2, also subjects with exclusion criteria present at inclusion but diagnosed only after birth will be retrospectively excluded from the FAS_{ENR} population.

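### The stated 91.8% power is correct for 100 vs 50 analysed fetuses, but the plan's own accrual reaches that size only at the top of its range and before exclusions; the 56% and 51% are true rates, not rates to be observed

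*SAP*

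**What the plan says.** SAP 1.5 and the Protocol's Sample size section carry the same text, apart from a citation for the 30% rate.

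- Target: "The aim is to include at least 100 fetuses in the FAV 1+2 groups and 50 in the comparison group no-FAV 1+2".
- Power at 60% vs 30%, by a two-sided Fisher's exact test at the 0.05 level: "a power of 91.8% would be able to be achieved". With 100 vs 100 the stated power is 98.7%.
- For at least 80% power at 100 vs 50: "a success rate of 56% vs 30% in the FAV and no-FAV group, respectively, would be needed to be observed". The 100 vs 100 scenario has the same sentence with 51%.
- Accrual: "it is estimated that 10-20 intervention cases can be included each year", with no-FAV cases projected at no less than half that number.
- Stop: at 100 FAV and at least 50 no-FAV enrolled, "or 5 years from the first included patient, whichever occurs first".

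The confirmatory test is run on FAS_ENR (SAP 4.1 and 4.6.1). SAP 2.1.1 says of the high-risk fetuses: "Therefore this subpopulation will be excluded from the full analysis set and analysed separately". It expects them to be over-represented in the FAV group. It also removes wrongly included cases and those whose exclusion criterion is found only after birth. The Protocol's data analysis section adds: "Cases with termination of pregnancy after study inclusion will be excluded from analysis but numbers noted".

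**The concern.** The power is quoted for a number of enrolled fetuses, and the test is done on a smaller set. The Protocol's exclusion section lets high-risk fetuses into the study for separate analysis, so they count towards the 100 and 50 but not in the primary comparison. No inflation for this is given. The time limit can also end the study below target, yet the only scenarios powered are the target and a larger one.

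This matters for reading a null result. The Protocol's closing section on clinical relevance says that existing programmes may need reconsideration if no benefit is shown. A reader would weigh such a result against a stated chance of 8.2% (100 − 91.8) of missing a true 30-point difference. The real chance could be several times that.

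The sentence on 56% and 51% is a separate, smaller fault. It presents a design assumption as a result that the data must show.

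**Working it through.** **Inputs (SAP 1.5).** Success 60% vs 30%; two-sided alpha 0.05; Fisher's exact test; 10 to 20 FAV per year; no-FAV at least half of FAV; 5-year limit.

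**Step 1: reproduce the plan's figures.** The arcsine approximation with continuity correction is

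power = Φ( √(4·n1·n2/(n1+n2)) · d − 1.96 ), with d = asin√(p1 − 1/(2·n1)) − asin√(p2 + 1/(2·n2)).

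For 100 vs 50: √(4·100·50/150) = 11.547 and d = 0.2905, so Φ(3.354 − 1.96) = 91.8%. For 100 vs 100 it gives 98.7%. Both match the plan. Full enumeration of the exact test gives 92.7% and 98.9%.

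For the 80% statements, the same approximation gives, at 100 vs 50, 79.1% for a true FAV rate of 55% and 82.3% for 56%. At 100 vs 100 it gives 78.9% for 50% and 82.7% for 51%. So 56% and 51% are also correct, as true rates in whole percentage points. (Enumeration gives 81.3% already at 55% with 100 vs 50; that is a difference of method, not an error.)

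**Step 2: accrual over 5 years.** FAV: 5 × 10 = 50 to 5 × 20 = 100. No-FAV, at the projected minimum of half: 25 to 50. At 15 per year: 75 and 37 (37.5 rounded down).

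**Step 3: power at 60% vs 30% by accrual and loss.** The documents give no share for any exclusion, so the losses are assumptions, taken as equal in both groups. The exact test by enumeration gives:

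| FAV per year | No loss | 20% loss | 30% loss |
|---|---|---|---|
| 20 | 100/50: 92.7% | 80/40: 85.1% | 70/35: 81.2% |
| 15 | 75/37: 85.1% | 60/30: 76.5% | 52/26: 65.1% |
| 10 | 50/25: 67.4% | 40/20: 50.8% | 35/17 to 35/18: 47.7% to 52.2% |

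Exact Fisher power moves in small steps with sample size, so differences of a point or two carry no meaning. The approximation that reproduces 91.8% is lower at the smaller sizes: 81.0% at 75/37 and 61.1% at 50/25.

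**Step 4: losses in FAV only**, the direction SAP 2.1.1 expects. From a full 100/50: 80/50 = 92.2% and 70/50 = 89.9%.

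**Step 5: what would have to be observed.** Unadjusted Fisher p-values against an observed 30% in no-FAV:

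- 100 vs 50: 47/100 vs 15/50 gives p = 0.054; 48/100 gives p = 0.037; 56/100 gives p = 0.003.
- 100 vs 100: 44/100 vs 30/100 gives p = 0.057; 45/100 gives p = 0.041.

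Significance is therefore reached well below an observed 56% or 51%.

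**The case against.** The plan states its power conditionally on the numbers included. It calls the calculation simplified, says that it is meant only to show that the study has potential, and notes that adjusted analyses will be needed. The condition is rare and the design observational. At 20 FAV per year the target can be enrolled in time, and half as many controls is a minimum, so more controls could raise power. At mid-range accrual, power before exclusions is still 81% to 85%.

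Most of this stands, and it limits the point. But the caveat about simplification concerns unknown confounders. It does not cover the 5-year stop or the gap between enrolled and analysed fetuses.

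A reader might infer more than the documents support:

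- That 91.8%, 98.7%, 56% or 51% is miscalculated. All four reproduce (step 1).
- That the study must fall short. This is certain only if accrual is below 20 per year or some fetuses are excluded.
- That the exclusions by themselves destroy power. From a full 100/50 they do not (steps 3 and 4).
- That 56% works as a success threshold. No decision rule uses it; SAP 4.1 and 4.6.1 rest on the adjusted logistic regression at the 0.05 level.
- That the SAP itself removes terminations from FAS_ENR. Its text does not say so; that exclusion comes from the Protocol.

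**Conclusion.** The point holds in this limited form. The 91.8% is right for 100 vs 50 analysed, and the plan's own projections reach 100/50 enrolled only at the top of the accrual range, before any removal from FAS_ENR. With controls at half of FAV, power before exclusions is about 93%, 85% and 67% at 20, 15 and 10 FAV per year. At the low end, a true 60% vs 30% difference would be missed about one time in three (100 − 67.4 = 32.6%). With an assumed equal loss of 0% to 30%, the whole range is about 48% to 93%, and slow accrual accounts for most of the fall.

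These figures rest on the plan's success rates, the minimum control projection, assumed loss shares and an unadjusted test. The effect of confounder adjustment on power is not quantified in the documents or here. In the 56% and 51% sentences only the reference to observed rates is wrong.

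**What to change.** In SAP 1.5 and the Protocol's Sample size section:

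1. State that 91.8% applies to 100 vs 50 fetuses analysed in FAS_ENR, not enrolled.
2. Add a power table for 10, 15 and 20 FAV per year over 5 years, crossed with assumed losses to FAS_ENR of 0% to 30%. Label the losses as assumptions and name the method (exact enumeration or approximation). With controls at half of FAV, exact enumeration spans about 48% to 93%. A row with more controls could be added.
3. For both 56% and 51%, say that this would need to be the true success rate for at least 80% power. The numbers stay.

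The cost is text and one table, and a less favourable stated power. No change to recruitment, analysis set or test is asked for.

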2 STUDY POPULATIONS

2.1 Definition of Study Populations

2.1.1 Full Analysis Set for All Enrolled

Fetuses with severe MR and severe LA enlargement and/or intact or highly restrictive interatrial communication and/or cases with hydrops present at inclusion are all high-risk cases regarding survival, but may have a rather good prognosis if they survive the first critical period. It is likely they will be overrepresented in the FAV group to such a degree that it will be difficult to control for through propensity score matching. Therefore this subpopulation will be excluded from the full analysis set and analysed separately. Fetuses developing any of these conditions after inclusion will not be excluded from the full analysis set.

All enrolled fetuses that have satisfied inclusion/exclusion criteria and belong to FAV 1+2 and no-FAV 1+2 groups and not listed as belonging to the high-risk population described above will be included in the Full Analysis Set enrolled (FAS_{ENR}) population. Infants wrongly included in the study (not fulfilling all inclusion or fulfilling any of the exclusion criteria) will not be part of the FAS_{ENR} population, but will be described in the safety analyses. As detailed under 1.3.2, also subjects with exclusion criteria present at inclusion but diagnosed only after birth will be retrospectively excluded from the FAS_{ENR} population.

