#### **Exclusion criteria**

- 1. Any associated cardiac defect except persistent left superior vena cava and coarctation of the aorta
- Any significant (i.e. that might influence outcome) extracardiac anomaly and/or known chromosomal aberration. Also, if such a condition is present at inclusion but diagnosed only after birth the case will be retrospectively excluded.

Endocardial fibroelastosis is accepted. Cases with severe mitral regurgitation and left atrial enlargement with or without restrictive or intact atrial communication and with or without hydrops will be included but analyzed as a separate group (17). Also cases with atrial septal balloon dilatation or stent placement will be included if the first intervention was aortic valvuloplasty or if no fetal aortic valvuloplasty was performed.

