1.3.2 Exclusion criteria

- 1. Any associated cardiac defect except persistent left superior vena cava and coarctation of the aorta.
- 2. Any significant (i.e. that might influence outcome) extracardiac anomaly and/or known chromosomal aberration. Also, if such a condition is present at inclusion but diagnosed only after birth the case will be retrospectively excluded.

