Effect of fetal aortic valvuloplasty on outcomes

Protocol No:

screening policies) and gestational age at inclusion. Most probably they are highly correlated and in that case the more influential of the two will be used.

Variables listed under 3.1 as potential confounders will be investigated whether they are important for discriminating FAV vs no-FAV and whether they are confounders (associated p<0.10 both to the group and the outcome).

Dichotomous outcome variables will be analysed using logistic regression, adjusted for identified confounders available at the time of study inclusion. Odds-ratios (OR) with 95% confidence intervals (CI) will be presented.

Time-to-event analyses will be performed using Cox proportional hazards models adjusting for identified confounders. Proportional hazards assumption will be checked by visually reviewing log(-log(survival)) vs log(time) graphs, and by adding interaction between treatment group and log(time) in the model, where significant interaction indicates non-proportionality. Other methods will be applied, e.g. Poisson regression for time varying data, allowing study of changes in treatment effects over follow-up time, in case non-proportionality of hazards occurs.

Time-to-event data will be described by using Kaplan-Meier technique.

The primary analyses for the FAV vs no-FAV group conducted on FAS_{ENR} population will be considered as confirmatory analyses and a total significance mass of 0.05 will be applied. The tests will be performed on the primary variable and the most important secondary variables using fix sequential testing procedure according to the following order:

1. Primary variable: Transplantation-free survival from fetal diagnosis to 2 years postnatal age, having a biventricular circulation without pulmonary hypertension at that time

2. Secondary variable: Transplantation-free survival from fetal diagnosis to 2 years of age

3. Secondary variable: Survival from fetal diagnosis to live birth at term (≥37 weeks)

4. Secondary variable: Proportion of included fetuses who have a biventricular circulation at neonatal hospital discharge

5. Secondary variable: Proportion of included fetuses who have a biventricular circulation at 2 years of postnatal age

This means that first test must be significant on 0.05 significance level in order to be able to further confirm the tests 2 to 5, and the second test must be significant on 0.05 level in order to be able to confirm tests number 3 to 5, etc.

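### Removing cases from the confirmatory set for conditions diagnosed only after birth is open to outcome-aware judgement, and no planned analysis of the primary variable is specified to keep them

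*SAP*

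**What the plan says.** The protocol, under Exclusion criteria, attaches a late-diagnosis clause to criterion 2 (extracardiac anomaly or chromosomal aberration): "Also, if such a condition is present at inclusion but diagnosed only after birth the case will be retrospectively excluded". SAP 1.3.2 repeats this. Criterion 2 reads "Any significant (i.e. that might influence outcome) extracardiac anomaly and/or known chromosomal aberration". Criterion 1, "Any associated cardiac defect except persistent left superior vena cava and coarctation of the aorta", carries no such clause in either document.

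SAP 2.1.1, citing 1.3.2, applies the rule to the enrolled full analysis set: "also subjects with exclusion criteria present at inclusion but diagnosed only after birth will be retrospectively excluded". The sentence before it already removes infants wrongly included, described as "not fulfilling all inclusion or fulfilling any of the exclusion criteria", with no limit on when this is discovered. SAP 2.1.2 also drops wrongly included infants from FAS_BIRTH. SAP 2.1.6 keeps them in the safety population.

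SAP 4.1 says that the FAV vs no-FAV analyses "conducted on FAS_{ENR} population will be considered as confirmatory analyses". SAP 4.6.1 gives the primary analysis as adjusted logistic regression for FAV 1+2 vs no-FAV 1+2, with propensity-matched Fisher tests as the sensitivity analyses.

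**The concern.** Birth comes after the decision on valvuloplasty, so this rule lets events after exposure decide who is counted in the confirmatory comparison. Three features make that more than a formality.

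- **Detection is unlikely to be equal.** A live-born infant is examined. A fetus that dies in utero may never be diagnosed and then remains as a failure. Death within 24 hours of the procedure can occur only in the FAV group, so the mechanism can act differently by group.
- **The decision is partly discretionary.** Whether an extracardiac anomaly might influence outcome, and whether it was present at inclusion, are judgements. The documents do not say who makes them, list qualifying conditions, set a cut-off date for this decision, or mask the decision to group or 2-year outcome. The only masking described is the core laboratory's remeasurement without sight of submitted values.
- **The effect would not be visible.** No analysis of the primary variable is specified to retain the removed cases, so a reader could not tell whether the removals shaped the result.

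The wording also leaves the scope open. If SAP 2.1.1 is read literally, associated cardiac defects found on the neonatal echo are removed too. If it is read through its cross-reference to 1.3.2, they are not removed by this rule. Two analysts could build different confirmatory sets.

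**Working it through.** **Inputs from the documents** (Protocol Sample size; SAP 1.5): 100 FAV and 50 no-FAV, success 60% vs 30%, two-sided Fisher's exact test at 0.05, stated power 91.8%.

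**Assumptions** (the documents give no figures): late-diagnosed prevalence q of 3% to 10%; no success among affected cases; fetal death d of 5% to 15% in FAV and 2% to 3% in no-FAV. The counts in step 3 are also assumed.

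**1. The plan's own figure.** Full enumeration of Fisher's test over both binomials gives 92.7% (92.0% with the doubled-tail p-value), close to the stated 91.8%. No stated figure is disputed.

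**2. Survival path alone.** Suppose true success s among unaffected fetuses is the same in both groups, all affected live-born infants are removed, and all affected fetuses that die in utero stay as failures. The observed rate is then s(1−q) / [(1−q) + q·d].

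- Largest case, q=0.10, s=0.60: FAV (d=0.15) 0.540/0.915 = 0.5902; no-FAV (d=0.03) 0.540/0.903 = 0.5980; difference −0.8 percentage points.
- Smallest case, q=0.03, s=0.30: FAV (d=0.05) 0.2910/0.9715 = 0.2995; no-FAV (d=0.02) 0.2910/0.9706 = 0.2998; difference −0.03 points.

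The shift is under 1 point. It runs against FAV when FAV has more fetal deaths.

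**3. Discretionary removal** (two-sided Fisher, unadjusted):

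| FAV | no-FAV | Change | p |
|---|---|---|---|
| 47/100 | 15/50 | none | 0.054 |
| 47/97 | 15/50 | 3 FAV failures removed | 0.036 |
| 47/97 | 15/49 | 3 FAV and 1 no-FAV failures removed | 0.051 |
| 48/100 | 15/50 | none | 0.037 |
| 48/100 | 15/48 | 2 no-FAV failures removed | 0.075 |
| 48/96 | 15/48 | 4 FAV and 2 no-FAV failures removed | 0.035 |
| 46/100 | 15/50 | none | 0.078 |
| 46/97 | 15/50 | 3 FAV failures removed | 0.052 |
| 60/100 | 15/50 | none | 0.0009 |
| 60/100 | 15/40 | 10 no-FAV failures removed | 0.024 |

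Two or three removals from one group can move a borderline result across 0.05 in either direction. Roughly proportional removal does not, and neither does removing ten no-FAV failures at the planned effect.

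**4. Cost of keeping everyone.** Diluting both rates by (1−q) at 100 vs 50:

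- q=3%: 58.2% vs 29.1%, power 91.4%
- q=5%: 57.0% vs 28.5%, power 90.5%
- q=10%: 54.0% vs 27.0%, power 87.9%

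An analysis that keeps all cases stays well above 80% power before confounder adjustment.

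**The case against.** The rule is prespecified, appears in the protocol itself, and is the same for both groups. It targets a condition present at inclusion, which is a baseline attribute, and it keeps the cohort on isolated aortic stenosis. The SAP separates baseline from later events elsewhere: fetuses that develop a high-risk condition after inclusion stay in FAS_ENR. All of this stands, and it makes dropping the rule from the main analysis debatable.

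A reader might infer four stronger points that the documents do not support.

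- *The SAP widens the protocol rule.* The sentence in 2.1.1 opens by citing 1.3.2, SAP section 6 reports no significant changes from the protocol, and the protocol's Study design section already has postnatal echoes reviewed to confirm eligibility. This is an ambiguity to reconcile, not a demonstrated extension.
- *The decisions are unblinded, and infants who do badly are investigated more.* The documents are silent on masking and on intensity of investigation. Both are plausible, but neither is stated.
- *An intrauterine death always stays as a failure.* Diagnosis after birth does not exclude post-mortem diagnosis, and the preceding sentence of 2.1.1 has no time limit.
- *The outcome-influence judgement governs the whole rule.* It qualifies the extracardiac anomaly. It is not clearly attached to chromosomal aberration and is not part of criterion 1.

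It is also fair that the p-value reversals need borderline counts and one-sided removal, and that the primary analysis is an adjusted regression, not Fisher's test. What remains is the undefined decision process and the absence of any analysis that retains the removed cases.

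**Conclusion.** The point holds as a gap in procedure and transparency, and it should be corrected before database lock. Removal from FAS_ENR after birth is partly post-exposure, rests on judgement for extracardiac anomalies, has no described masking, and is not tested by any planned analysis of the primary variable.

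On size, unequal detection through fetal death moves the group difference by 0.03 to 0.8 percentage points under the assumed ranges. Discretionary removal matters more, because two or three cases from one group can decide a borderline result. A result near 60% vs 30% would survive it. A reader might take the reversals as evidence of bias, but no net bias or direction is shown; they show only how little it takes when p is close to 0.05. Under the fixed-sequence procedure in SAP 4.1, a changed first test also decides whether tests 2 to 5 can be confirmed.

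**What to change.** 1. **SAP 2.1.1 and 2.1.2.** State which criteria the late-diagnosis rule covers, consistent with SAP 1.3.2 and the protocol. Change both the late-diagnosis sentence and the wrongly-included sentence before it; editing only the former leaves the latter removing the same infants. Make the same change in 2.1.2.
2. **Decision process.** Have existing study personnel decide every late exclusion from the diagnosis alone, masked to group and 2-year outcome, before database lock. Treat post-mortem findings in the same way as findings in live-born infants, without telling the decider which source applies.
3. **SAP 4.6.1.** Add a sensitivity analysis of the primary variable, using the same adjusted logistic regression for FAV 1+2 vs no-FAV 1+2, that keeps all enrolled fetuses eligible on information available at inclusion (prenatal findings plus core-laboratory review of the baseline echo). Require the confirmatory conclusion to be reported alongside it.
4. **Listing.** Report every late exclusion by group, with diagnosis and outcome.

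The cost is wording changes, a short masked review, one extra model run and one listing. The added analysis slightly dilutes both success rates; the confirmatory analysis can stay as prespecified.
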